5.3 Safety Assessments

Bleeding is the primary safety outcome measure. Bleeding AEs/SAE/s will be assessed by the investigator at every post-surgery visit. At discharge from the hospital, impress upon the subject and/or caregiver the importance of contacting the Investigator immediately if subject experiences signs of clinically over bleeding during the treatment period or the follow-up period. These bleeding AEs/SAEs will be evaluated by the clinical events adjudication committee.

Acute clinically overt bleeding is defined as new onset, visible bleeding or signs or symptoms suggestive of bleeding with confirmatory imaging techniques which can detect the presence of blood (eg, US, CT, MRI).

All acute clinically overt bleeding events will be adjudicated by the ICAC as a major bleeding event, a clinically relevant nonmajor bleeding event or neither.

The definition of major bleeding described below is adapted from the International Society on Thrombosis and Hemostasis (ISTH) definition.

Major Bleeding Event is defined as a bleeding event that is:

- Acute clinically overt bleeding accompanied by one or more of the following:
 - A decrease in hemoglobin (Hb) of 2 g/dL or more over a 24-hour period
 - A transfusion of 2 or more units of packed red blood cells
 - Bleeding that occurs in at least one of the following critical sites:
 - Intracranial
 - Intra-spinal
 - Intraocular (within the corpus of the eye; thus, a conjunctival bleed is not an intraocular bleed)
 - Pericardial
 - An operated joint and requires re-operation or intervention
 - Intramuscular with compartment syndrome
 - Retroperitoneal.
- Bleeding that is fatal.

Clinically Relevant Nonmajor Bleeding event is defined as a bleeding event that is:

- Acute clinically overt bleeding
- Does not satisfy additional criteria required for the bleeding event to be defined as a major bleeding event and meets at least one of the following criteria.
- Epistaxis (nose bleed):
 - Subject seeks medical attention from a physician
 - Subject visits an emergency room
 - Bleeding requires an intervention, eg, nasal pack
 - Single bleeding episode persists for 5 minutes or more.
- Gastrointestinal Bleed:
 - Vomit containing frank blood or coffee ground material which tests positive for blood
 - Endoscopically confirmed bleeding
 - Frank blood per rectum or melanic stools.
- Hematuria:
 - Overt, spontaneous bleeding
 - Bleeding (bloody urine) persists for 24 hours or more after instrumentation.
- Bruising/ecchymosis:
 - Any bruise which is assessed as “unusual” (eg, greater than expected following surgery).
- Hemoptysis:
 - Expectoration of blood or blood-stained sputum.
- Hematoma:
 - Overt blood collection associated with the surgical wound
Presence of a hematoma is demonstrated radiographically, eg, US, CT, MRI, and a drop in hemoglobin is present with no external evidence of bleeding.

Fatal Bleeding Event is defined as a bleeding event that the ICAC determines is the primary cause of death or contributes directly to death.

5.4 Efficacy Assessments

No specific diagnostics are required for evaluating asymptomatic VTE's. However, patients with signs or symptoms suggestive of deep vein thrombosis (DVT) or pulmonary embolism (PE) must be evaluated with the clinically appropriate imaging techniques, including compression ultrasound (CUS) or venography for suspected DVT, or VQ scanning or spiral CT for suspected PE. Additional diagnostics performed outside the efficacy assessments and outside SAE reporting need not be part of the study report but should be maintained as part of the medical record.

An independent events adjudication committee will evaluate these reports of VTEs as well as of deaths. All deaths will be adjudicated regardless of whether they seem related to VTE's or not. In

case of death, all efforts should be made to determine the cause of death which is aligned to the BMS process on data collection, obtaining autopsy reports or verbal information from family.

5.4.1 Primary Efficacy Assessment

The composite of VTE/all cause death will include all adjudicated symptomatic pulmonary embolisms and deep vein thromboses. Statistical details will be described in the Statistical Analysis Plan as a separate document.

5.4.2 Secondary Efficacy Assessments

Not Applicable.

5.5 Other Assessments

VTE's that are discovered as part of incidental findings (such as CT scans for other parts of the body), will not be counted towards the efficacy endpoint but will be adjudicated and reported separately.

6 ADVERSE EVENTS

An *Adverse Event (AE)* is defined as any new untoward medical occurrence or worsening of a pre-existing medical condition in a patient or clinical investigation subject administered an investigational (medicinal) product and that does not necessarily have a causal relationship with this treatment. An AE can therefore be any unfavorable and unintended sign (including an abnormal laboratory finding, for example), symptom, or disease temporally associated with the use of investigational product, whether or not considered related to the investigational product.

Adverse events can be spontaneously reported or elicited during open-ended questioning, examination, or evaluation of a subject. (In order to prevent reporting bias, subjects should not be questioned regarding the specific occurrence of one or more AEs.)

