3.1.3 Treatment Period

The day of surgery is Day 1.

The first dose of apixaban will be administered 12 - 24 hours after completing skin wound closure, typically in the morning of Day 2 and then BID for 35 ± 2 days for the subjects undergoing total hip replacement or 12 ± 2 days for the subjects undergoing total knee replacement.

While hospitalized, subjects will be evaluated on Day 1, Day 2 and discharge day for suspected symptomatic VTE, bleeding events or any AEs or SAEs.

At any subsequent treatment visits (Day 7 ± 2 and Day 12 ± 2 for TKR subjects or Day 7 ± 2 and Day 35 ± 2 for THR subjects), subjects will be instructed to report to the investigator all AEs, including signs and/or symptoms suggestive of VTE and any bleeding events they experienced since their last visit. Subjects with signs and/or symptoms of VTE at any time should return to the hospital/clinic and undergo appropriate diagnostic evaluation.

If study medication is discontinued for a suspected DVT and or PE, alternative antithrombotic prophylaxis may be initiated per the Investigator's discretion and standard of care. Every effort

must be made to confirm a suspected DVT and/or PE diagnosis before discontinuing study medication and initiating treatment per the Investigator's standard of care.

Samples for laboratory assessment of hematology will be obtained on the day of discharge.

Urine pregnancy test will be performed on Day 12 for TKR subjects and on Day 35 for THR subjects.

Dosing Diaries should be collected at Day 7 & Day 12 for TKR subjects and at Day 7 & Day 35 for THR subjects.

Subjects should be encouraged to return for an in person visit on Day 7 and Day 12 for TKR and Day 7 and Day 35 for THR. Alternatively those visits would be performed by phone.

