8.3 Endpoint Definitions

Primary Endpoint:

The primary study endpoint is a composite of International Society on Thrombosis and Haemostasis (ISTH) major bleeding/clinically relevant non-major bleeding (CRNM) in subjects undergoing elective total knee or hip replacement at the end of treatment + 2 days, where ISTH major bleeding is

- Fatal or
- Bleeding in a critical organ, such as brain, spine, eye, retroperitoneum, joint, heart sac, or skeletal muscle (and resulting in compartment syndrome), or
- Bleeding that results in a fall of hemoglobin of 2 g/dL or more or transfusion of 2 units or more of packed red cells or whole blood within 24 hours

and CRNM bleeding is bleeding that

- Is clinically acute and overt
- Does not satisfy criteria as a major bleed but requires medical intervention, such as a visit to a physician's office, emergency room, or urgent care center for epistaxis.

Secondary Endpoints:

The secondary endpoint will be: The composite of VTE/all cause death at the end of treatment + 2 days, where VTE is the combination of deep vein thrombosis and non-fatal pulmonary embolism.

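### Section 6 bars questions about specific adverse events without exempting bleeding, the primary endpoint; the in-hospital assessment frequency is also stated two ways

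*Protocol*

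**What the plan says.** **The general AE rule.** Protocol Section 6 describes how adverse events come to light: "Adverse events can be spontaneously reported or elicited during open-ended questioning, examination, or evaluation of a subject". It then adds, in parentheses and with prevention of reporting bias as the reason, that "subjects should not be questioned regarding the specific occurrence of one or more AEs". No endpoint is exempted.

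**The bleeding provisions.** Under 5.3, bleeding AEs and SAEs "will be assessed by the investigator at every post-surgery visit" and then go to adjudication. At discharge, sites are to "impress upon the subject and/or caregiver the importance of contacting the Investigator immediately" if signs of bleeding appear. Section 3.1.3 has subjects instructed at treatment visits to report "any bleeding events they experienced since their last visit", and 3.1.4 has them asked to report bleeding at follow-up. Any of these post-discharge visits may be held by telephone. Tables 5.1-1 and 5.1-2 have a row for Symptomatic VTE Assessment but none for bleeding, which therefore falls under AE/SAE Assessment.

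**The CRNM definitions.** The list in 5.3 includes items that a subject may be the only one to notice, such as, for a nosebleed, "Single bleeding episode persists for 5 minutes or more", and for hemoptysis, "Expectoration of blood or blood-stained sputum". Protocol 8.3 and SAP 4.1 are narrower: "Does not satisfy criteria as a major bleed but requires medical intervention".

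**In-hospital frequency.** The synopsis has inpatients evaluated every day for VTE and bleeding. Section 3.1.3 names Day 1, Day 2 and the day of discharge, and both schedule tables agree with 3.1.3.

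**The concern.** The primary endpoint reaches the analysis by way of AE reporting, and the section that governs AE reporting tells sites not to ask about particular events. The provisions on bleeding tell subjects to report and investigators to assess, but none says that staff may put a direct question, gives a standard one, or overrides Section 6. A site that asks only how the subject has been, and a site that asks about nosebleeds, blood in urine or sputum and unusual bruising, could both claim to follow the protocol.

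The study estimates an absolute bleeding rate, and the SAP wants to call that rate acceptable. There is no comparator in which the same under-reporting would occur, so a bleed that is not elicited lowers the result directly. The confidence interval reflects sampling error only. Adjudication cannot recover an event that was never reported.

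The two in-hospital frequencies are a separate matter of wording, but they concern the same endpoint: the protocol does not say consistently how often bleeding is assessed before discharge.

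**Working it through.** **1. The passages side by side**

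| Place in Protocol | Direction to site or subject | Settles whether a direct bleeding question is allowed? |
|---|---|---|
| 6 | Open-ended elicitation, examination or evaluation; no questions on specific AEs | Reads as no; bleeding not exempted |
| 3.1.3 | Subjects instructed to report bleeding since the last visit | Prompts for bleeding; no question stated |
| 3.1.4 | Subjects asked to report AEs, bleeding included | Prompts for bleeding; no standard question |
| 5.3 | Investigator assesses bleeding at each post-surgery visit; counselling at discharge | Requires assessment; method not stated |
| 5.2 | Diary records study medication; worksheets and eCRFs supplied | Diary: no. Worksheets and eCRFs not shown |

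**2. Which events are exposed**

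- Major bleeds, and bleeds that led to medical care, leave other traces and are much less exposed.
- If the 5.3 list governs, a five-minute nosebleed or blood-stained sputum at home counts as CRNM, and the site may learn of it only from the subject. By telephone, examination is not possible.
- If 8.3 and SAP 4.1 govern, such an event does not count without medical intervention, so the exposure is much smaller.

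**3. The plan's own figure** (Protocol 8.1, SAP 5: N = 500, rate 4.36%, 95% CI 2.6% to 6.2%, width 3.6%)

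- Half-width = 1.96 × √(0.0436 × 0.9564 / 500) = 1.79 percentage points.
- Interval: 4.36 ± 1.79 = 2.57% to 6.15%, width 3.58%. This agrees with the plan up to rounding; 22/500 = 4.4% gives 2.6% to 6.2%.
- Expected events: 500 × 0.0436 = 21.8, about 22.

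**4. Effect of a missed event**

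- 1 / 500 = 0.2 percentage points per event.
- One half-width corresponds to 1.79 / 0.2 ≈ 9 events. This is a yardstick only. The documents give no capture rate, none is assumed here, and so no total loss is computed.

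**5. Gap between the last two scheduled treatment contacts** (3.1.3; assumes discharge by Day 7)

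- THR: 35 − 7 = 28 days; shortest 33 − 9 = 24, longest 37 − 5 = 32.
- TKR: 12 − 7 = 5 days; shortest 10 − 9 = 1, longest 14 − 5 = 9.

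These are intervals between contacts. They are not periods in which reporting depends on recall alone, because 5.3 has subjects told to call at once if they bleed.

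**6. In-hospital frequency**

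The two statements differ only for inpatient days after Day 2 and before discharge. Length of stay is not given, so the number of days affected is unknown.

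**The case against.** The case for leaving Section 6 alone is substantial. The sentence is a general AE rule, worded as advice and placed in parentheses. The bleeding provisions are more specific, and the instruction in 3.1.3 is itself a prompt about bleeding. Subjects are also told to report promptly between visits and are given discharge instruction and emergency cards. The eCRFs, worksheets, site training and adjudication guidelines are not shown and may already contain a standard question, so divergence between sites is inferred, not documented. Much of the exposure depends on a different problem, the two CRNM definitions. And Section 6 gives a reason for its rule: in an open-label study, prompting can bring in trivial events.

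Most of this stands, and it limits the point. It rules out the stronger reading that a reader might take from Section 6, namely that the protocol prevents bleeding from being ascertained or that the primary rate is bound to be too low. Sections 3.1.3, 3.1.4 and 5.3 contradict that. It also rules out reading the 28-day THR gap as 28 days of unaided recall.

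What it does not do is resolve the conflict of wording. No sentence exempts bleeding, and the schedules leave bleeding inside the activity that Section 6 governs. The reporting-bias argument favours one uniform question over a choice left to each site, and adjudication is there to sort minor events from CRNM events.

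On the in-hospital frequency, the objection is that the discharge assessment, with its hemoglobin test, closes the interval. That is fair, and the documents do not support an inference that bleeds between Day 2 and discharge go unrecorded. The two statements still disagree.

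**Conclusion.** The point holds in a limited form, with medium confidence. Section 6 states a rule that, read literally, conflicts with how the primary endpoint is meant to be collected. Its likely effect is confined to patient-reported CRNM bleeds, mainly at telephone contacts and mainly if the 5.3 list governs. Each event lost costs 0.2 percentage points on a planned rate of 4.36% (about 22 events, half-width 1.8 points), and no total can be derived. The conclusion assumes that the unseen eCRFs and worksheets do not already hold a standard question; if they do, only a cross-reference is missing.

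A reader might also infer a parallel gap for VTE. The documents do not show one: the schedules give symptomatic VTE its own assessment row at every post-surgery contact.

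The daily versus Day 1, Day 2 and discharge conflict is real and minor. The change to Section 6 should be made, but the gap does not undermine the study.

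**What to change.** **Section 6.** Add after the restriction: *This restriction does not apply to bleeding, the primary endpoint. At every post-surgery contact, telephone included, all subjects are asked the same standard bleeding question, worded to the bleeding endpoint definition in this protocol.* Write the question only after the CRNM wording of Protocol 5.3 has been reconciled with that of Protocol 8.3 and SAP 4.1. If the eCRF or worksheets already hold such a question, refer to it here instead. No added DVT or PE question is needed.

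**In-hospital evaluation.** Reconcile the synopsis with 3.1.3 and Tables 5.1-1 and 5.1-2, so that one frequency for assessing bleeding and VTE before discharge appears throughout.

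**Cost.** A protocol amendment with IRB/IEC approval (9.1.1), two sentences, one short question on the existing visit form, site training, and one wording reconciliation. No visit is added. The downside is that the reported CRNM rate may be somewhat higher and that prompting may bring in more minor events, which the adjudication committee would have to sort.

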6.1 Serious Adverse Events

A *serious AE (SAE)* is any untoward medical occurrence that at any dose:

- results in death
- is life-threatening (defined as an event in which the subject was at risk of death at the time of the event; it does not refer to an event which hypothetically might have caused death if it were more severe)
- requires inpatient hospitalization or causes prolongation of existing hospitalization (see **NOTE** below)
- results in persistent or significant disability/incapacity
- is a congenital anomaly/birth defect
- is an important medical event (defined as a medical event(s) that may not be immediately life-threatening or result in death or hospitalization but, based upon appropriate medical and scientific judgment, may jeopardize the subject or may require intervention [eg, medical, surgical] to prevent one of the other serious outcomes listed in the definition above.)
Examples of such events include, but are not limited to, intensive treatment in an emergency room or at home for allergic bronchospasm; blood dyscrasias or convulsions that do not

result in hospitalization.) Potential drug induced liver injury (DILI) is also considered an important medical event. (See [Section 6.6](#) for the definition of potential DILI.)

Suspected transmission of an infectious agent (eg, any organism, virus or infectious particle, pathogenic or non-pathogenic) via the study drug is an SAE.

Although pregnancy, overdose, cancer, and potential drug induced liver injury (DILI) are not always serious by regulatory definition, these events must be handled as SAEs. (See [Section 6.1.1](#) for reporting pregnancies.)

NOTE:

The following hospitalizations are not considered SAEs in BMS clinical studies:

- a visit to the emergency room or other hospital department < 24 hours, that does not result in admission (unless considered "important medical event" or event life threatening)
- elective surgery, planned prior to signing consent
- admissions as per protocol for a planned medical/surgical procedure
- routine health assessment requiring admission for baseline/trending of health status (eg, routine colonoscopy)
- medical/surgical admission for purpose other than remedying ill health state and was planned prior to entry into the study. Appropriate documentation is required in these cases
- admission encountered for another life circumstance that carries no bearing on health status and requires no medical/surgical intervention (eg, lack of housing, economic inadequacy, care-giver respite, family circumstances, administrative).

6.1.1 *Serious Adverse Event Collection and Reporting*

Following the subject's written consent to participate in the study, all SAEs, whether related or not related to study drug, must be collected, including those thought to be associated with protocol-specified procedures. All SAEs must be collected that occur during the screening period and within 30 days of discontinuation of dosing. The investigator should report any SAE occurring after these time periods that is believed to be related to study drug or protocol-specified procedure.

An SAE report should be completed for any event where doubt exists regarding its status of seriousness.

If the investigator believes that an SAE is not related to the study drug, but is potentially related to the conditions of the study (such as withdrawal of previous therapy, or a complication of a study procedure), the relationship should be specified in the narrative section of the SAE Report Form.

SAEs, whether related or not related to study drug, and pregnancies must be reported to BMS (or designee) within 24 hours. SAEs must be recorded on the SAE Report Form; pregnancies on a Pregnancy Surveillance Form (electronic or paper forms). When using paper forms, the reports are to be transmitted via email or confirmed facsimile (fax) transmission to:

SAE Email Address: See Contact Information list.

SAE Facsimile Number: See Contact Information list.

For studies capturing SAEs/pregnancies through electronic data capture (EDC), electronic submission is the required method for reporting. The paper forms should be used and submitted immediately, only in the event the electronic system is unavailable for transmission. When paper forms are used, the original paper forms are to remain on site.

SAE Telephone Contact (required for SAE and pregnancy reporting): See Contact Information list.

If only limited information is initially available, follow-up reports are required. (Note: Follow-up SAE reports should include the same investigator term(s) initially reported.)

If an ongoing SAE changes in its intensity or relationship to study drug or if new information becomes available, a follow-up SAE report should be sent within 24 hours to BMS (or designee) using the same procedure used for transmitting the initial SAE report.

All SAEs should be followed to resolution or stabilization. In case of death, all efforts should be made to determine the cause of death which is aligned to the BMS process on data collection, obtaining autopsy reports or verbal information from family.

6.2 Nonserious Adverse Events

A *nonserious adverse event* is an AE not classified as serious.

6.2.1 Nonserious Adverse Event Collection and Reporting

The collection of nonserious AE information should begin at initiation of study drug.

Nonserious AEs should be followed to resolution or stabilization, or reported as SAEs if they become serious (see [Section 6.1.1](#)). Follow-up is also required for nonserious AEs that cause interruption or discontinuation of study drug, or those that are present at the end of study treatment as appropriate. All identified nonserious AEs must be recorded and described on the nonserious AE page of the CRF (paper or electronic).

Completion of supplemental CRFs may be requested for AEs and/or laboratory abnormalities that are reported/identified during the course of the study.

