8.4.3 Safety Analyses

Bleeding is the primary safety outcome measure. The event rate of adjudicated major bleeding or clinically relevant non-major bleeding events during the treatment period will be summarized. Subgroup analyses by surgery type will also be conducted.

An additional analysis will summarize all adjudicated major bleeding or clinically relevant non-major bleeding occurring during the treatment period, which begins with the first dose of study medication.

In addition, an analysis of major or clinically relevant non-major bleeding events will look at the bleeding events that occur prior to the administration of apixaban. Additional details will be provided in the Statistical Analysis Plan.

The incidence of adverse events and of marked abnormalities in clinical laboratory tests will be summarized by treatment group for both the treatment and follow-up period.

All adverse events that are serious or that result in discontinuation of study therapy will be described in depth. K-M estimator will be used to estimate the rate of early discontinuation due to any reason.

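### Protocol 6.2.1 starts nonserious AE collection at first dose, in conflict with the Day 1 evaluation in 3.1.3 and the pre-apixaban bleeding analysis in 8.4.3, which could be undercounted

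*Protocol*

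**What the plan says.** Protocol 6.2.1 sets the start of nonserious AE collection: "The collection of nonserious AE information should begin at initiation of study drug". Protocol 6.1.1 starts SAE collection at written consent. Protocol 3.1.3 defines Day 1 as the day of surgery and has the first dose "administered 12 - 24 hours after completing skin wound closure, typically in the morning of Day 2", so Day 1 normally lies before dosing.

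Two places need nonserious bleeding information from before that dose:

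- Protocol 3.1.3, for hospitalized subjects: "subjects will be evaluated on Day 1, Day 2 and discharge day for suspected symptomatic VTE, bleeding events or any AEs or SAEs".
- Protocol 8.4.3: "an analysis of major or clinically relevant non-major bleeding events will look at the bleeding events that occur prior to the administration of apixaban". It adds: "Additional details will be provided in the Statistical Analysis Plan".

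Two others point the same way, less firmly. The AE/SAE row in Tables 5.1-1 and 5.1-2 is marked at Enrollment and at Surgery Day 1. Protocol 5.3 states, with no first-dose limit: "All acute clinically overt bleeding events will be adjudicated by the ICAC".

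The CRNM criteria in 5.3 include a hematoma described as "Overt blood collection associated with the surgical wound" and a bruise judged unusual, for instance "greater than expected following surgery".

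On the analysis side, SAP 7.6 summarizes adjudicated bleeding in the Treatment Period, which SAP 6.1 opens at first dose. SAP 6.1 also defines an Intended Treatment Period that opens at enrollment, but no visible analysis uses it. Several SAP sections refer to a Core SAP that is not among the documents.

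**The concern.** The protocol gives sites two different start points for the same information. A site working from 6.2.1 may leave a nonserious wound hematoma on the evening of surgery off the AE page. A site working from 3.1.3 and the schedule would record it. Both could say they followed the protocol.

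The item at stake is the pre-apixaban bleeding analysis. In the visible documents it is the only planned look at bleeding after surgery and before drug, in a study with no comparator arm. Its definition includes CRNM events, which is the category most likely to be nonserious. An incomplete count would make early post-surgical bleeding look rarer than it was, to a degree that could depend on each site's reading.

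**Working it through.** This is mainly a check of one passage against others. The protocol gives no figure for pre-dose bleeding.

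**1. The plan's only design figure.** Protocol 8.1 and SAP 5 give n = 500, p = 4.36% and a 95% CI of (2.6%, 6.2%), width 3.6%. The Wald interval is p ± 1.96 × √(p(1 − p)/n) = 0.0436 ± 1.96 × √(0.0436 × 0.9564/500) = 0.0436 ± 0.0179. That is 2.57% to 6.15%, width 3.58%. It agrees with the plan apart from rounding of the upper limit (6.2% follows from 4.4% + 1.8%). Nothing here changes it: Protocol 8.2 counts events from first dose.

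**2. The passages side by side.**

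| Place | What it implies for a nonserious bleed before first dose |
|---|---|
| Protocol 6.2.1, start rule | Collection has not begun |
| Protocol 6.2.1, later sentence | Any nonserious AE that is identified goes on the CRF page |
| Protocol 3.1.3 | Subject is evaluated on Day 1 for bleeding and any AE |
| Protocol 8.4.3 | Event is needed if it is CRNM or major |
| Tables 5.1-1 and 5.1-2 | AE/SAE assessment at Enrollment and Day 1, nonserious part not spelled out |
| Protocol 5.3 | Bleeding AEs assessed at every post-surgery visit; all overt bleeds adjudicated; no recording start given |

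The firm conflicts are with 3.1.3 and 8.4.3.

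**3. Length of the affected post-surgery window.** It is 12 to 24 hours per subject. For 500 dosed subjects: 500 × 12 h = 6,000 h = 250 subject-days, and 500 × 24 h = 12,000 h = 500 subject-days. This measures the window, not the bias.

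**4. Direction and form of the undercount.** Let r be the true pre-dose major/CRNM rate and s the share of those events that are serious. If only serious events were recorded, the recorded count would be 500 × r × s and the fraction missed 1 − s. The documents give neither r nor s, so the values below are assumptions.

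| r | True events | s = 10% | s = 25% | s = 50% | s = 75% |
|---|---|---|---|---|---|
| 1% | 5 | 0.5 | 1.25 | 2.5 | 3.75 |
| 2% | 10 | 1.0 | 2.5 | 5.0 | 7.5 |
| 4% | 20 | 2.0 | 5.0 | 10.0 | 15.0 |

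If a fraction f of events arises at sites using the literal start rule, the recorded count is 500 × r × [1 − f(1 − s)]. With r = 2%, s = 25% and f = 50% this is 10 × (1 − 0.5 × 0.75) = 6.25 of 10. For any values of s and f between 0 and 1 the error is zero or downward.

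**5. Denominator.** Protocol 8.2 and SAP 6.2 base safety summaries on subjects who received study drug. A subject who bled after surgery and was never dosed would be left out by default. Protocol 3.4.2 lists persistent bleeding after surgery among the reasons for stopping study drug, so such omissions might not be random; how many there would be is not given. The SAP's Enrolled Population is everyone who signed consent, which can include subjects never operated on. No visible text says which population serves the pre-apixaban analysis.

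**The case against.** The best defence is in 6.2.1 itself, which goes on to require that every identified nonserious AE be recorded. A bleed found at the Day 1 evaluation has been identified, so a careful site would record it. Section 6 also defines an AE in terms of a subject who has been given the product, so a dosing-based start for nonserious events is not arbitrary. Serious bleeds are collected from consent, an SAE report is due when seriousness is in doubt, and prolonged hospitalization makes an event serious. The adjudication committee's remit in 7.2 covers suspected major, CRNM and minor bleeds and is not tied to the nonserious AE page. The combined AE/SAE schedule row could mean SAEs only before dosing. The analysis affected is descriptive, with no hypothesis or threshold.

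Much of this stands. It makes the loss possible rather than certain, limits it to nonserious events, and weakens the schedule and 5.3 as evidence. It does not remove the conflict: the start rule remains at odds with the Day 1 evaluation of any AE in 3.1.3, and 8.4.3 depends on CRNM events that need not be serious.

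A reader might also infer that the SAP has dropped the analysis promised in 8.4.3. The documents do not establish that. SAP 6.1 defines a period opening at enrollment, and the Core SAP may hold the analysis and its denominator. What can be said is that the visible SAP does not show them.

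**Conclusion.** The conflict is real and worth correcting. Protocol 6.2.1 cannot be squared with 3.1.3 as written, and it leaves 8.4.3 without an assured source for nonserious pre-dose bleeds. The possible loss is confined to nonserious, mainly CRNM, events before first dose; it can only run downward and may vary by site. Its size cannot be estimated: under the literal start rule the missed fraction is the nonserious share of those events, anywhere from 0 to 100%.

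Two stronger readings are tempting and not supported. One is that the primary bleeding rate is biased. It is not, because its window runs from first dose to two days after the last dose. The other is that the on-treatment rate loses its reference. No passage plans a comparison of pre-dose with on-treatment bleeding.

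**What to change.** In Protocol 6.2.1, add an exception: acute clinically overt bleeding events as defined in 5.3, serious or not, are recorded with date and time of onset and sent to the ICAC from the start of the pre-apixaban window analysed in 8.4.3. State that start, for example enrollment or start of surgery, consistently with Tables 5.1-1 and 5.1-2. Starting only at wound closure would leave out earlier bleeds that 8.4.3 and those assessments would cover. Reconcile the general start time for nonserious AEs with 3.1.3.

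In SAP 7.6, add the pre-apixaban major/CRNM summary with its window and denominator, so that operated subjects who bled and were never dosed are not dropped by default, or cite the Core SAP section that holds it. If the denominator is operated subjects, dosed or not, SAP 6.3 needs a line defining that population.

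The cost is a sentence or two in the protocol, a population line and one table in the SAP. No visits or tests are added. The downside is some additional nonserious bleeds to record and adjudicate.
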